### **Brief video-based education: an underutilized but promising medium for behavior change in the context of the HIV/AIDS epidemic in Africa**

Brief video-based health interventions have demonstrated effectiveness in promoting behavior change and acquisition of health knowledge in a variety of clinical settings. Studies have demonstrated that video-based educational interventions increase knowledge about HIV and other STDs, promote partner disclosure, influence attitudes supporting safer sex behaviors, and improve treatment compliance. The use of video as an educational vehicle offers several advantages:

1. Video interventions are highly cost-effective requiring limited ongoing resources after content creation. A cost-effectiveness evaluation of a video based HIV education program demonstrated an annual savings of greater than US \$5million for 10,000 patients in averted HIV infections.
2. Videos are not subject to inter-user variability. Therefore core messages can be pre-tested and standardized to maximize knowledge acquisition.
3. Videos do not require additional hiring of staff, with only minimal training required for existing staff, and may indeed liberate HCW time for other activities thereby offering ancillary benefits to the health system.
4. Videos are well-suited for promoting health behavior change in settings with low literacy such as Malawi.
5. Videos readily engage participants improving adoptability. Messages can be carefully crafted and woven into entertaining and dramatic story lines, and pre-tested to ensure cultural/linguistic sensitivity. The result is a consistently high-quality and motivating messaging.
6. Videos can be highly effective if delivered at critical stress-inducing “teachable moments”, such as the period after HIV diagnosis and prior to ART initiation.

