## OBJECTIVES AND HYPOTHESES

At present no published clinical trial has reported the use of video-based interventions to improve HIV treatment related patient outcomes in low-resource countries. The proposed research addresses a question critical to optimize PMTCT service delivery and will also provide needed data regarding the impact of inexpensive, scalable video-based interventions in the field of HIV prevention and treatment. Our specific aims and hypotheses are:

**Specific aim 1: To evaluate the effectiveness of VITAL start on improving partner outcomes (disclosure, testing, and linkage to ART), maternal retention and ART adherence via a multi-site, parallel group (n=446 each group), randomized controlled, outcome assessor blinded trial.**  
We hypothesize that: the proportion of partners who are disclosed to, receive HIV testing, and are linked to ART will be higher in the intervention vs. control group at 3 months follow-up and; the proportion of women retained in care (**primary outcome**) and adherent to ART (self report, and undetectable viral load) at 12 months after ART initiation will be higher in the intervention vs. control group.

[figure not shown]
**Specific aim 2: To critically examine the delivery of VITAL start** via in-depth interviews and surveys administered to patients, partners, and health workers. Adoption of and satisfaction with the program will be measured. Qualitative interviews will be utilized to obtain feedback on motivational qualities of the program and benefits and challenges of delivery.

**Specific aim 3: To assess the cost-effectiveness of the VITAL start intervention.** Cost-effectiveness will be assessed using incremental cost-effectiveness ratios, with health effects expressed in terms of viral load suppression and costs of resources used for the intervention.

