#### **Sample Size Calculation:**

The primary outcome for this study is a composite outcome of retention in care and maternal viral suppression that has been used in similar previous studies. This outcome was selected to measure the ultimate goal of ART use within PMTCT services: to keep HIV+ mothers engaged in care and virally suppressed to maximize the benefits of ART for both treatment and prevention. This outcome assumes that those not retained are not virally suppressed. The sample size calculation is

based on a comparison of the proportions of those in the intervention versus SOC arms reaching the combined primary endpoint at 12 months after maternal ART initiation. Pearson Chi-square test for Proportion Difference was used for calculation. A combination of various scenarios was considered for retention in care (50-90%), maternal viral suppression (50-90%) among those retained, and contamination rate (0-15%). A difference of 15% was selected as the smallest difference that would be of clinical significance. It is also assumed that an effect of this magnitude could be anticipated in this field of research.

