to differences in the cultural context; (3) point out areas in which interviewing techniques could be improved; and (4) identify recurrent themes. We will use standard qualitative content analysis approaches for thematic analysis of the transcripts. Study staff experienced in qualitative data analysis will code the scripts and establish a coding scheme. The developed coding scheme will be refined to enable one research team member to independently code the remaining transcripts, with revisions made as necessary to reflect new and evolving themes. Thematic analysis will occur concurrently with data collection to allow further exploration and clarification of emergent ideas, and data collection will continue until data saturation is reached. Transcribed interviews and digital files will be stored on a password-protected computer, and when not in use will be stored under lock and key. All data will be anonymized for publication. Only researchers affiliated with the study will have access to participant data.

---

**Specific aim 3: To assess the cost-effectiveness of the VITAL start intervention.** Cost-effectiveness will be assessed using incremental cost-effectiveness ratios, with health effects expressed in term of viral load suppression and costs of resources used for the intervention.

---

**Costing:** The MOH will be the main implementer of the VITAL start intervention as well as standard of care pre-ART counseling. Therefore, we will assess costs from the provider (MOH) perspective. We will use both micro and macro based approaches as appropriate to identify and quantify intervention resources. Retrospectively, we will extract information on resources expended for video design and production from inventory and other BCM-CFM Tingathe program documents. Unit prices will be obtained from accounts records or from local retailers.

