Prospectively, we will collect information regarding costs of administering both the VITAL start and the SOC pre-ART counseling. To measure staff time devoted to pre- ART counseling, we will perform time-motion assessments in line with the STAMP (Suggested Time and Motion Procedures). We will sample sufficiently to account for potential sources of heterogeneity such as study clinic and provider. We will randomly sample provider sessions from each arm of the study and each participating study clinic during every month of participant enrolment. A minimum of 4 assessments will be conducted per clinic every month. Therefore, we anticipate collecting data on over 200 pre-ART counseling sessions. Repeat sampling of providers is expected and will be recorded. The value of staff time will then be estimated as the product of their gross salary and share of time allocated to intervention/pre ART counseling.

**Cost effectiveness analysis:** We will calculate incremental cost-effectiveness ratio (ICER), for the primary outcome of economic interest: proportion of women virally suppressed at 6 months follow up. The ICER is the difference in costs between two interventions divided by the difference in their effects, and can be interpreted as the incremental price of a unit health effect from the intervention under study, as compared to the alternative.

We will conduct one way and multi-way sensitivity analysis to model cost-effectiveness under various conditions, such as lower pricing of video production, mode of delivery, tablets, and alternate health care workers cadres to deliver the intervention. Finally, we will conduct probabilistic sensitivity analysis using bootstrapping methods to ascertain robustness of our results to extreme assumptions/scenarios. Based on emerging literature, we will define VITAL start as cost-effective if its ICER is < 50% of Malawi GDP ( $0.5 \times \$250 = \$125/\text{YLS}$ ), compared to standard pre-ART counseling. We will also consider alternative thresholds of 100% and 300% of GDP.

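### Aim 3 compares a cost per additional woman virally suppressed with a threshold per YLS, and no conversion links the two

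*Combined protocol and SAP*

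**What the plan says.** The Objectives and Hypotheses section sets up Aim 3 "with health effects expressed in terms of viral load suppression". The Aim 3 introduction in the data analysis plan repeats this: "with health effects expressed in term of viral load suppression and costs of resources used for the intervention".

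Under Cost effectiveness analysis, the primary economic outcome is the "proportion of women virally suppressed at 6 months follow up". The ICER is the cost difference divided by the effect difference, and it "can be interpreted as the incremental price of a unit health effect from the intervention under study".

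The same subsection then gives the decision rule: "we will define VITAL start as cost-effective if its ICER is < 50% of Malawi GDP". The plan evaluates this as half of $250, that is $125 per YLS. It adds: "We will also consider alternative thresholds of 100% and 300% of GDP". The abbreviation YLS appears only in this rule and is not spelled out.

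**The concern.** The only ICER the plan defines is in dollars per additional woman suppressed. The threshold it must fall below is in dollars per YLS. The two can be compared only through a figure for the life-years gained per additional woman suppressed, and the plan gives none.

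The yes/no label is the only decision criterion stated for Aim 3. If the ICER falls in a certain range, that label depends on an assumption nobody has written down. It could be wrong in either direction: an intervention could be called cost-effective when it misses the life-year threshold, or the reverse.

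**Working it through.** **The plan's own figure.** 0.5 × $250 = $125, which reproduces exactly. The $250 is evidently GDP per person. The alternatives are 1 × $250 = $250 and 3 × $250 = $750. The arithmetic is sound; the fault is in the units.

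**Unit check.**

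- ICER = (difference in cost per woman) / (difference in proportion suppressed) = dollars per additional woman suppressed.
- Threshold T = dollars per YLS.
- Let L be the life-years gained per additional woman suppressed. Then ICER per YLS = ICER / L.

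**Is L given anywhere?** The aims, the Outcome Measures section with Table 3, the data analysis plan and the costing text contain no life-year outcome for Aim 3, survival model, time horizon, discount rate or conversion factor. The examples listed for the sensitivity analyses are video price, delivery mode, tablets and health worker cadre. The probabilistic analysis is a bootstrap, which captures sampling variation and does not supply L. The source cited at the decision rule supports the threshold, not a conversion. Each woman's planned follow-up is 12 months, so life-years would need a model.

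**When the label changes** (costlier and more effective):

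- Literal rule passes if ICER < T.
- Converted rule passes if ICER / L < T, that is ICER < T × L.
- The two disagree when the ICER lies between T and T × L, and agree otherwise. The literal rule equals the converted rule only at L = 1.

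Assuming L = 0.5 and L = 2, the intervals of disagreement, in dollars per additional woman suppressed, are:

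| T | L = 0.5 | L = 2 |
|---|---|---|
| $125 | $62.50 to $125 | $125 to $250 |
| $250 | $125 to $250 | $250 to $500 |
| $750 | $375 to $750 | $750 to $1,500 |

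**Expressed as incremental cost per woman counselled** (ICER × gain), at T = $125. The documents give no incremental cost and no expected 6-month gain. The 15 points below is borrowed from the Sample Size Calculation ("A difference of 15% was selected as the smallest difference that would be of clinical significance"), where it refers to the 12-month composite. The 5 points is an assumption.

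- Gain 0.15: 62.5 × 0.15 = $9.38; 125 × 0.15 = $18.75; 250 × 0.15 = $37.50. Labels differ from $9.38 to $18.75 (L = 0.5) or $18.75 to $37.50 (L = 2).
- Gain 0.05: 62.5 × 0.05 = $3.13; 125 × 0.05 = $6.25; 250 × 0.05 = $12.50. Labels differ from $3.13 to $6.25 (L = 0.5) or $6.25 to $12.50 (L = 2).

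**Worked cases at T = $125.**

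| Extra cost / gain | Literal ICER | At L = 0.5 | At L = 2 |
|---|---|---|---|
| $20 / 0.15 | $133.33, fails | $266.67, fails | $66.67, passes |
| $2 / 0.15 | $13.33, passes | $26.67, passes | $6.67, passes |
| $40 / 0.05 | $800, fails | $1,600, fails | $400, fails |

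The label changes only in the first case. If the extra cost is zero or negative and suppression improves, no threshold is needed.

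**The case against.** The strongest reply is that the authors intended a separate life-year ICER for the threshold step and left out how to obtain it. Calling 6-month suppression the primary economic outcome leaves room for another. But none is named, and the rule refers to the intervention's own ICER, of which only one is defined. The remedy is the same on either reading: state the model or drop the rule.

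A second reply is that the problem may never arise. The background describes video as "requiring limited ongoing resources after content creation", and a VITAL start session takes about 37 minutes against typically one hour for the flipchart. If the intervention costs no more and suppresses more women, it needs no threshold. This stands as a possibility. Video production is to be costed, however, and tablets are a named cost input, so the saving is not assured. A pre-specified rule has to work when it fails to appear. A cheaper but less effective result would also need its own rule, because a criterion of ICER below T does not carry over directly.

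A third reply is that three thresholds are planned, so the conclusion need not rest on one. All three share the mismatch. Moving from $125 to $750 could imitate some values of L above 1 but none below 1, and the plan does not present them in that way.

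It is also fair that the dollar illustrations rest on assumed costs, gains and values of L. They show that the label can change, not that it is likely to.

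**Conclusion.** The point holds. The decision threshold is in a different unit from the ratio it judges, and nothing in the documents connects them. For a costlier and more effective intervention, the label depends on the unstated L whenever the ICER lies between T and T × L. How likely that is cannot be judged from the documents, which give no L, no incremental cost and no expected 6-month effect. The conclusion also relies on reading YLS as year of life saved.

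The consequence is confined to Aim 3's yes/no statement. The ICER, its cost sensitivity analyses, the bootstrap and the efficacy analyses are unaffected. It should be fixed, but it does not threaten the trial's main result.

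**What to change.** 1. Report the trial-based ICER as dollars per additional woman virally suppressed at 6 months, and remove the per-YLS rule for that ratio.
2. To present it without a cut-off, an acceptability curve over a range of willingness to pay per additional woman suppressed is one option. It can come from the bootstrap already planned.
3. Apply the 50%, 100% and 300% of GDP thresholds only if a stated model converts suppression to life-years, giving its source, horizon, discounting and uncertainty.
4. Spell out YLS.

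Steps 1 and 4 are rewording, with no new data and no change to the 6-month economic outcome. Because the plan already reports enrolment as finished at 800, the change should be dated and justified; the data analysis plan provides for documenting changes and their rationale in the study report. The downside is losing the yes/no label unless a life-year model is added, which is extra work and brings its own assumptions. A threshold stated directly per additional woman suppressed would keep a label, but it would need a justification that the documents do not supply.

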## **RISKS/BENEFITS TO SUBJECTS AND DEALING WITH ADVERSE EVENTS**

The risks to participating in this study are minimal and are primarily related to issues of confidentiality. Potential breach of confidentiality may occur, although multiple safeguards, as outlined below will be put into place to minimize this risk. Study participants may feel psychological distress during participant interviews. Although this has not been documented in other studies seeking to improve partner involvement, because the intervention does seek to promote partner involvement there may be

a risk of intimate partner violence. Participants may feel coercion to participate in the activities. By using an informed consent, all participants will be given sufficient information to make an educated decision about participation.

We are taking precautions to limit any emotional harm to participants that the interview process may cause patient participants. Consents will remind participants that they may decline to respond to any item(s) during study interviews, and may end study participation at any time without affecting the quality of health care they receive or current state of employment (HCW). We will ensure that mechanisms are in place in case participants experience intimate partner violence, distress or express suicidality on depression screens. Mechanisms will include counseling by study personnel, and referral to a psychosocial counselor trained in managing domestic violence and psychological issues.

Disclosure of medical or other personal information about participants, particularly HIV status and social issues such as intimate partner violence, may result in negative stigma being associated with the individual and/or family. We will take all possible precautions against breaches of confidentiality to minimize this risk (as explained in detail below).

#### **Potential benefits of the proposed research to human subjects and others**

Women in the intervention group may benefit from receiving the VITAL start intervention, which is designed to enhance partner engagement as well as self-management skills related to medication adherence. This in turn may decrease risk of mother-to-child HIV transmission, while maximizing maternal health. We believe the potential benefits outweigh the risks. Women in the control group may also benefit from participation in the baseline and follow-up surveys, which may encourage conversation between the women and her partner. All participants may receive a psychological benefit by talking to someone about their health care experiences. Likewise, health care providers, and key informants may receive psychological benefit by talking to someone about the challenges they have experienced while trying to provide PMTCT care. All participants may receive additional psychological benefit knowing that their participation may contribute to the understanding of new insights on barriers to care for PMTCT recipients. By contributing to the evidence base outlining high-yield and scalable approaches to improving PMTCT retention and partner involvement, this study offers a potential indirect benefit to other HIV-positive pregnant women.

HIV-positive pregnant women face barriers to involving their partners in PMTCT and remaining adherent to ART. Few theory-based behavioral interventions have been rigorously evaluated, and none that utilize videos. This is the first trial to examine the effects of a video-based intervention for partner engagement as well as HIV prevention and care amongst PLHIV in sub-Saharan Africa. By evaluating the efficacy of a brief facility-based video intervention, the research team will expand knowledge regarding effective ways to educate and promote behavior change amongst HIV+ pregnant women. Moreover, data gained from this study will help establish the feasibility and potential impact of video-based interventions as a means for health education and behavior change in resource-limited settings. With the global move towards universal ART treatment, and rising burden on health care providers, the need for evidence-based, inexpensive, scalable interventions that provide high quality pre-ART education and promote life-long adherence to treatment will be critical. This study will provide evidence regarding a potentially highly effective, cost-effective model: brief video-based interventions. This research will inform research on technology-based partner engagement and maternal adherence promotion interventions and will have broader implications on video-based interventions across health domains in sub-Saharan Africa.

#### **COSTS AND COMPENSATION:**

There are no costs to the participant for taking part in this research. However, transportation costs will be reimbursed at \$5 USD. In addition, they will also receive a small snack during the interview.

## **CONFIDENTIALITY ASSURANCES/ETHICAL CONSIDERATIONS**

All study participants will undergo informed consent by trained study staff, using IRB-approved informed consent forms in either Chichewa or English depend on participant preference. The consent form and study materials will be approved by the Institutional Review Board of the National Health Sciences Research Committee in Lilongwe, Malawi and by the Baylor College of Medicine Institutional Review Board.

We will take all possible precautions against breaches of confidentiality. All research personal will be trained in the need for absolute confidentiality. We acknowledge that a breach of confidentiality is possible, however we anticipate that the likelihood is very low given the precautions taken to protect confidentiality. Our efforts will include:

1. All staff will be trained in confidentiality and data security procedures using open-access standardized online modules provided by the Collaborative Institutional Training Initiative (CITI), a recognized leader in research training that is not affiliated with the study.
2. Privacy will be maintained by conducting all study procedures in private areas. Data will be rendered anonymous to the degree possible to minimize likelihood of any individual being identified. Only study identification numbers will be used for data abstraction and analysis. The only forms containing patient names will be informed consent forms, and these will be secured in a locked cabinet only accessible to key personnel.
3. All electronic data will be password protected and stored in a password protected and encrypted computer secured in a locked cabinet when not in use. Only select devices maintained with password protections and encryption will be allowed access to study data.
4. Data transfer will only occur over encrypted networks.
5. All analysis will be conducted only on de-identified data.

## **INFORMED CONSENT**

***Informed consent*** will be obtained from all patients, partners, and health care providers. Consent forms with information regarding the study have been translated from English to Chichewa and then back-translated into English by a co-investigator fluent in Chichewa who has experience translating study consents in Malawi. Consent will be obtained via the following procedure:

- 1) Health care providers will be given the written consent form to read. For patients or other participants who are unable to, or are uncomfortable with reading the consent study staff will read the form aloud to the patient. Study staff will periodically stop reading and will ask the patient if she has any questions. All participants will be encouraged to ask questions if they do not understand the information.
- 2) After the participant finishes reading the form, or the form has been read (patients), study staff will briefly summarize the information in the consent form and ask the participant if she/he has any questions. If the participant did not understand the information, the study staff will repeat and explain the specific information that was not understood.
- 3) After all questions have been answered to the satisfaction of the participant, the provider/key informant will be asked for their written agreement. For patients, if the participant is unable to sign their name, the study staff will obtain a thumbprint. The study staff will also sign, print, and date the form to acknowledge that the individual gave their verbal agreement. For patients who are illiterate, study staff will ensure that a witness is present during the consent process and the witness will also sign, print and date the form to acknowledge that the individual gave their verbal agreement.
- 4) Copies of both the English and Chichewa forms will be provided to those participants who wish to take a copy.

- 5) Consent forms will be kept for three years after the completion of the investigation and will be maintained according to GCP guidelines at a central location. The key will only be available to the PI and study staff.

